3.2. Secondary Endpoints

The following endpoints will be also evaluated as secondary endpoints:

- Rate of Major Adverse Event (MAE) Rate in hospital and at 30 days, 1, 2 and 3 years post-procedure, defined as a composite rate of cardiovascular death, index limb amputation and ischemia-driven Target Lesion Revascularization (TLR).
- Rate of occurrence of arterial thrombosis of the treated segment.
- Rate of ipsilateral embolic events of the study limb.
- Rate of clinically-driven target lesion revascularization at 6, 12, 24 and 36 months.
- Patency rate at 12 months post-procedure, defined as freedom from clinically driven TLR and duplex ultrasonography restenosis (ultrasound peak systolic velocity ratio ≤ 2.4 or stenosis ≤50%)
- Rate of vascular access site complication defined as the combined rate of hematoma, AV fistula or a pseudoaneurysm that required intervention, such as surgical repair or transfusion, prolonged hospital stay or required a new hospital admission.
- Lesion success (per device), defined as achievement of a final in-lesion residual diameter stenosis of <50% (by QA), using any device after wire passage through the lesion. Pre- and post-dilatation of the lesion with a non-study device is considered part of assigned device treatment.
- Technical success (per device), defined as achievement of a final in-lesion residual diameter stenosis of <50% (by QA), using the CVT Everolimus-coated PTA Catheter without a device malfunction after wire passage through the lesion. Preand post-dilatation are considered part of assigned device treatment.
- Clinical success (per subject), defined as technical success without the occurrence of major adverse events during the procedure.
- Procedural success (per subject), defined as lesion success without the occurrence of major adverse events during procedure.
- Ankle-Brachial Index (ABI) changes before procedure compared with ABI at discharge and at 6 and 12 months.

Confidential Page 16 of 79

- Change in WIQ (walking impairment questionnaire) from pre-intervention at 6 and 12-months follow-up.
- Change in walking distance from pre-procedure at 6 and 12 months.
- Change in Rutherford classification grades of chronic limb ischemia from preintervention at 6 and 12-months follow-up for the treated limb.

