5.2. Anticipated Adverse Events

An anticipated adverse event is any untoward medical occurrence in a subject which is predefined in the protocol and/or Instruction for Use (IFU) and that is identified or worsens during a clinical study, regardless whether or not the event is considered related to the study device or drug regimen prescribed as part of the protocol.

The following is a list of adverse events that may result from the PTA procedure.

- Abrupt closure
- Acute MI
- Allergic reaction to contrast, concomitant medications (Allergic Reaction)
- Amputation
- Aneurysm
- Arrhythmias (bradycardia & tachycardia)
- Arterial dissection
- Arterial perforation or rupture
- Artery spasm
- AV fistula
- Bleeding

Confidential Page 28 of 79

- Bypass graft surgery (emergent or non-emergent)
- Chest pain
- Death (cardiovascular or non-cardiovascular related)
- Discomfort during the procedure
- Embolism/PTA catheter embolism
- Endocarditis
- Fever
- Groin Bruising/Discomfort
- Hematoma
- Hemorrhage
- Hypertension
- Hypotension
- Injury to the groin blood vessel
- Infection or pain at insertion site
- Ischemia
- Nausea
- Pseudoaneurysm
- Renal failure
- Restenosis
- Sepsis /infection
- Stroke/CVA
- Wound complication or wound infection
- Thrombosis
- Total occlusion
- Vomiting / nausea

The oral formulation of everolimus has been evaluated in clinical trials and is approved worldwide for the prophylaxis of organ rejection in adult kidney transplant recipients at low-moderate immunologic risk and for the treatment of patients with advanced renal cell carcinoma. Oral dose of everolimus depending on the indication ranges between 1.5 and 20 mg/day. The following list includes the known risks of everolimus at these oral doses. The following is a list of theoretical adverse events that may result from the addition of everolimus to a PTA catheter:

- Abdominal pain
- Anemia
- Angioedema
- Anorexia
- Asthenia
- Constipation

Confidential Page 29 of 79

- Cough
- Delayed wound healing/fluid accumulation
- Diarrhea
- Dyslipidemia (including hyperlipidemia and hypercholesterolemia)
- Dyspnea
- Dysgeusia
- Dyspepsia
- Dysuria
- Dry skin
- Edema (peripheral)
- Epistaxis
- Fatigue
- Headache
- Hematuria
- Hyperglycemia
- Hyperlipidemia
- Hyperkalemia
- Hypertension
- Hypokalemia
- Hypomagnesemia
- Hypophosphatemia
- Increased serum creatinine
- Infections and serious infections: bacterial, viral, fungal, and protozoal infections
- Insomnia

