APPENDIX B: TRIAL ABBREVIATIONS AND DEFINITIONS

Trial Abbreviations

ABI Ankle-Brachial Index

ABR Angiographic Binary Restenosis

AE Adverse Event

aPTT Partial Thromboplastin Time

AV Arteriovenous
BMI Body Mass Index
CBC Complete Blood Count
CEC Clinical Events Committee
CI Clinically Indicated

CLI Critical Limb Ischemia

COPD Chronic Obstructive Pulmonary Disease

CRF Case Report Form
CT Computed Tomography
CVA Cerebrovascular Accident
CVD Cardiovascular Disease

CVT Chansu Vascular Technologies

EC Ethics Committee
GCP Good Clinical Practice

ICH International Conference on Harmonisation

ID Identification
IFU Instructions for Use

ISO International Organization for Standardization

ITT Intent-to-Treat Late Lumen Loss LLL Major Adverse Event MAE **MEC** Medical Ethics Committee Myocardial Infarction MI MLD Minimum Lumen Diameter Magnetic Resonance MR Peripheral Artery Disease PAD

PT Prothrombin Time

PTA Percutaneous Transluminal Angioplasty

QA Quantitative Angiography
RVD Reference Vessel Diameter
SAE Serious Adverse Event
SC Steering Committee
SFA Superficial Femoral Artery

SGOT Serum Glutamic-oxaloacetic Transaminase
SGPT Serum Glutamic Pyruvic Transaminase
TER Target Extremity Revascularization
TLR Target Lesion Revascularization
WIQ Walking Impairment Questionnaire

Confidential Page 53 of 79

Trial Definitions

Abrupt or Acute Closure

Quantitative Angiography findings or obstruction of contrast flow in the dilated segment where there had previously been a patent segment and documented anterograde flow. For an initial subtotal lesion, acute closure describes a total obstruction to arterial flow, either sustained or transient at the site of the treated lesion. In a situation where the dilated segment was closed or occluded at the beginning of the procedure, acute closure should only be used to describe the outcome if there was a period of vessel patency during the procedure documented by normal anterograde contrast flow beyond the lesion site with the PTA catheter removed from the vessel followed by closure before the patient was discharged from the catheterization laboratory.

Acute Success

Acute success is classified according to the following definitions:

Clinical Success

Clinical success (per subject) is defined as technical success without the occurrence of major adverse events during procedure.

Lesion Success

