The principle of including outcomes of all patients in the analysis who are enrolled into the clinical trial/investigation, regardless of the treatment actually received.

Late Lumen Loss (LLL)

Calculated as Minimum Lumen Diameter (MLD) post-procedure – MLD at follow-up

Mean in-lesion Late Loss will also be measured: (Mean In-lesion MLD, post-procedure) – (Mean In-lesion MLD at follow-up)

Lead Principal Investigator

A physician-specialist, related to the study, who is responsible for the overall conduct of the trial at all sites.

Major Adverse Event (MAE)

A composite rate of cardiovascular death, index limb amputation and ischemia-driven Target Lesion Revascularization (TLR).

Minimum Lumen Diameter (MLD)

The average of two orthogonal views (when possible) of the narrowest point within the area of assessment – in lesion, in stent or in segment. MLD is visually estimated during angiography by the Investigator; it is measured during QA by the Angiographic Core Lab.

Multilevel Disease

Presence of obstructive lesions at more than one level in the same extremity as the treatment lesion.

Myocardial Infarction (MI)

Q-wave MI (QMI) - Development of new pathological Q-waves in 2 or more contiguous leads (according to the Minnesota code) with or without post-procedure creatine kinase (CK) or CK-MB levels elevated above normal.

Occlusion

Incomplete vessel opacification distal to the lesion or if the distal vessel fills via collateral circulation.

Chronic Occlusion:

An occlusion presumed to have been present for at least 1 month prior to the procedure.

Total Occlusion:

An occlusion with no ante grade filling of contrast to the distal segment.

Patency Rate

Patency rate defined as freedom from clinically-driven TLR and from Duplex ultrasound or angiographic stenosis >50% at 6, 12, and 24 months.

Percent Diameter Stenosis

Confidential Page 58 of 79

The value calculated as 100 * (1 - MLD/RVD) using the mean values from two orthogonal views (when possible) by QA.

Popliteal Artery

Defined as the vessel located between Hunter's canal and the trifurcation of the anterior tibial, posterior tibial and peroneal arteries.

Primary Investigator

A physician responsible for conducting the clinical trial at each investigational site, which is responsible for the overall conduct of the trial at their site and compliance with protocol.

Reference Vessel Diameter (RVD)

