An approximation of the diameter of the vessel at the location of the target lesion. RVD is visually estimated during angiography by the Investigator and it is measured during QA by the Angiographic Core Laboratory.

Restenosis

Re-narrowing of the artery following the reduction of a previous narrowing. It is defined as the presence of a hemodynamically significant restenosis ($\geq 50\%$), as determined by angiography.

Rutherford/Becker Categories - Chronic Limb Ischemia

Category	Clinical Description	Objective Criteria
0	Asymptomatic, no hemodynamically significant occlusive disease	Normal results of treadmill*/stress test
1	Mild claudication	Treadmill* exercise complete, post exercise AP is greater than 50 mm Hg but more than 25 mm Hg less than normal
2	Moderate claudication	Symptoms between those of categories 1 and 3
3	Severe claudication	Treadmill* exercise cannot be completed post exercise AP is less than 50 mm Hg
4	Ischemic rest pain	Resting AP of 40 mm Hg or less, flat or barely pulsatile ankle or metatarsal plethysmographic tracing, toe pressure less than 30 mm Hg
5	Minor tissue loss, non-healing ulcer, or focal gangrene with diffuse pedal ischemia	Resting AP of 60 mm Hg or less, flat or barely pulsatile ankle metatarsal plethysmographic tracing flat or barely pulsatile, toe pressure less than 40 mm Hg
6	Major tissue loss, extending above transmetatarsal level, functional foot no longer salvageable	Same as category 5

^{*5} minutes at 3.2 km/h on a 12° incline

Worsening Rutherford Becker Clinical Category:

A deterioration (an increase) in the Rutherford Becker Clinical Category by more than 2 categories from the earliest post-procedural measurement or to a category 5 or 6.

Confidential Page 59 of 79

Revascularization

Target Lesion Revascularization (TLR):

Target lesion revascularization (TLR) is defined as any repeat percutaneous intervention of the target lesion or bypass surgery of the target vessel performed for restenosis or other complication of the target lesion.

Clinically Indicated (CI) Target Lesion Revascularization:

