A revascularization of the target lesion is considered clinically-indicated if angiography shows a percent diameter stenosis $\geq 50\%$ and there is worsening of the Rutherford Becker Clinical Category that is clearly referable to the target lesion. (worsening is defined as a deterioration (an increase) in the Rutherford Becker Clinical Category by more than 2 categories from the earliest post-procedural measurement or to a category 5 or 6.) An independent angiographic core laboratory should verify that the severity of percent diameter stenosis meets requirements for clinical indication and will overrule in cases where investigator reports are not in agreement.

Target Extremity Revascularization (TER)

Target extremity revascularization (TER) is defined as any percutaneous intervention or surgical bypass of any segment of the target extremity. The target extremity is defined as the ipsilateral limb arteries proximal and distal to the target lesion, which includes upstream and downstream branches and excludes the target lesion itself.

Serious Adverse Event (SAE)

An Adverse Event is considered serious if the event led, or might have led, to one of the following outcomes:

- Death of a subject
- Serious deterioration in the health of a subject that resulted in any of the following:
 - Life-threatening illness or injury
 - o Permanent impairment of a body structure or body function
 - o Hospitalization or prolongation of patient hospitalization
 - Medical or surgical intervention to prevent life-threatening illness or injury or permanent impairment to a body structure or body function
 - Chronic disease
- Foetal distress, foetal death or a congenital physical or mental impairment or birth defect

Note: Planned hospitalizations for pre-existing conditions or a procedure required by this protocol without serious deterioration in health is not considered a serious adverse event.

Successful Pre-Dilatation

Pre-dilatation has been successfully completed without complications if all of the following apply:

- Diameter stenosis $\leq 70\%$ (by visual estimate)
- Lesion length still within the requirements of the protocol/CIP
- No angiographic complications

Superficial Femoral Artery (SFA)

Confidential Page 60 of 79

The SFA connects to the popliteal artery at the opening of adductor magnus or hunter's canal towards the end of the femur.

Thrombosis

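### The MAE condition in clinical and procedural success is nearly inert, and the analysis set drops the one event most likely to trigger it

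*Combined protocol and SAP*

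**What the plan says.** Section 3.2 lists four acute success endpoints. Technical and lesion success are per device and require a final in-lesion residual stenosis below 50% by quantitative angiography. The other two build on them: "Clinical success (per subject), defined as technical success without the occurrence of major adverse events during the procedure" and "Procedural success (per subject), defined as lesion success without the occurrence of major adverse events during procedure". The synopsis carries the same two definitions. Appendix B repeats the one for clinical success, "Clinical success (per subject) is defined as technical success without the occurrence of major adverse events during procedure", but has no entry for procedural success.

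Appendix B defines an MAE as "A composite rate of cardiovascular death, index limb amputation and ischemia-driven Target Lesion Revascularization (TLR"). Its entry for TLR reads "any repeat percutaneous intervention of the target lesion or bypass surgery of the target vessel performed for restenosis or other complication of the target lesion". A clinically indicated TLR also needs a stenosis of at least 50% and a Rutherford category that worsens "by more than 2 categories from the earliest post-procedural measurement or to a category 5 or 6". Ischemia-driven TLR, the term used in the MAE, has no definition of its own.

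Section 6.4 analyses all secondary endpoints in the per-treatment evaluable population. Section 6.2 defines the evaluable population as subjects without a bailout procedure and with at least one valid follow-up visit. Section 5.1 starts adverse event reporting once the index procedure is complete, whereas Table 2 and Appendix F tick adverse events in the procedure column.

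**The concern.** A reader of the report will take clinical success to mean a good angiographic result achieved safely. The only safety element is the MAE condition, and its window closes with the procedure. If hardly any MAE can fall inside that window, two of the four acute success rates look like safety-adjusted results but are not. The evaluable-population rule adds to this: the event most likely to fall inside the window also removes the subject from the denominator. In a first-in-human study (Section 9.6) the early success figures will be read closely, so their labels should match what they measure.

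**Working it through.** The plan states no expected rate for these endpoints, so there is no figure to reproduce. The check takes each MAE component in turn and then sizes what remains.

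**1. Which components can occur during the procedure?**
- *Ischemia-driven TLR.* TLR is a repeat intervention. Post-dilatation and bail-out stenting belong to the index procedure (Section 4.3). If ischemia-driven is read as clinically indicated, the main test compares against a post-procedural Rutherford reading, first scheduled before discharge (Section 4.5, Table 2). The exception is bypass of the target vessel for another complication of the target lesion. An emergency bypass in the same session is not strictly excluded.
- *Index limb amputation.* Nothing excludes it, but it is not plausible within an angioplasty session in Rutherford 2 to 4 subjects.
- *Cardiovascular death.* Possible. Section 5.2 lists death among events that may result from the procedure, and Appendix J row 3f gives it as a peri- and post-procedure hazard.

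**2. How often would death trigger the condition?** Inputs: N = 75 (Section 6.3); rate p between 0.1% and 1% (Appendix J row 3f), read as a rate per subject.
- Expected deaths, N × p: 75 × 0.001 = 0.075 and 75 × 0.01 = 0.75.
- Chance of at least one, 1 − (1 − p)^75: 7.2% at 0.1% and 52.9% at 1%.

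These are upper bounds for the window, because the band also covers deaths after the procedure.

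**3. What would one death do to the rate?** Suppose every other subject is a technical success and evaluable.
- Counted as a failure among all 75: 74/75 = 98.7%, exact 95% CI 92.8% to 99.97%. Without a death: 75/75 = 100%, CI 95.2% to 100%. The difference is 1/75 = 1.3 percentage points.
- Under Sections 6.2 and 6.4 as written: the subject has no follow-up visit and leaves the set, giving 74/74 = 100%. The lower exact limit is 0.025^(1/74) = 95.1%. The death leaves no mark on the reported success rate.

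**4. Is the event recorded?** Read literally, Section 5.1 begins adverse event reporting just as the success window ends. Table 2 and Appendix F say otherwise.

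**5. Can the rates differ for another reason?** Yes, because the unit changes from device to subject and up to two study catheters are allowed (Section 3.5, criterion 9). Let s be the share of subjects with two devices and q the success rate per device. Assume independent devices and that both must succeed. Success per subject is then (1 − s)q + sq², and the gap is sq(1 − q). With s = 25% and q = 95%, success per subject is 93.8%, a gap of 1.2 points. For s from 0 to 50% and q from 90% to 98%, the gap is 0 to 4.5 points. The plan gives neither s nor q; both are assumptions.

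**The case against.** The strongest reply is that little is lost. MAEs in hospital and at 30 days, thrombosis of the treated segment and ipsilateral embolic events are separate endpoints in Section 3.2. The primary six-month safety endpoint uses the safety population, so a procedural cardiovascular death counts there. An uncorrected closure or occlusive thrombus at the lesion already fails the stenosis criterion, and with it all four success endpoints. The composites are descriptive endpoints in a feasibility study, and no hypothesis, decision rule or power figure rests on them. All of this stands and keeps the point small.

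A reader might infer that clinical and procedural success merely repeat technical and lesion success. The documents do not support that: procedural death is possible, emergency bypass is not strictly ruled out, and the change of unit can separate the figures with no MAE at all. That last difference says nothing about safety, however.

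What the reply does not answer is the label. Other endpoints hold the early events, but the two composites that claim to combine result and safety cannot reflect them.

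**Conclusion.** The point holds in a limited form. The MAE condition is nearly inert, not void by definition. It would be triggered realistically by a cardiovascular death during the procedure, with fewer than one expected in 75 subjects, or arguably by an emergency bypass. As planned, the death would be excluded instead of counted as a failure.

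A reader might go further and say that a subject who dies before discharge is reported as a success. Sections 6.2 and 6.4 point the other way: that subject is dropped. Nor is early safety information missing from the trial as a whole; it is missing from these two composites.

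The conclusion rests on four assumptions: ischemia-driven TLR is judged broadly as clinically indicated TLR; the per-treatment evaluable population of Section 6.4 is the evaluable population of Section 6.2; the pre-discharge assessment is not a follow-up visit (Section 4.6 places follow-up after discharge); and the Appendix J band applies per subject. No sample-size or power figure changes.

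**What to change.** 1. In the synopsis, Section 3.2 and the clinical success entry of Appendix B, replace *during the procedure* with *through hospital discharge*. This matches the in-hospital MAE endpoint already planned.
2. State in Section 6.4 that both composites are analysed on the safety population, so that procedural and in-hospital cardiovascular deaths count as failures. Without this step the longer window would still lose them. The in-hospital MAE rate falls under the same Section 6.4 rule and needs the same population if the figures are to agree.
3. Reconcile Section 5.1 with Table 2 and Appendix F on when adverse event reporting starts.

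It would also help to say how two devices combine into one result per subject.

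The in-hospital data are already planned, so the cost is a few wording changes. The downside is that reported success rates may be slightly lower. The safety population also brings back subjects who had a bailout procedure, which should be stated beside the result. I would not add complications filmed under Appendix M as failures: which of them should count is debatable, and thrombosis and embolic events already have their own endpoints.

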3.3. Study Population

Subjects included in this study will be comprised of male and female subjects derived from the general interventional radiology or angiology population. The study will include seventy-five (75) subjects with a superficial femoral and/or populated (P1 segment) artery target lesion(s) eligible to be treated by interventional therapy and who meet all the inclusion criteria and none of the exclusion criteria of this study.

3.4. Ethical Considerations

The trial will be conducted in accordance with this Clinical Investigational Plan (CIP), the Declaration of Helsinki, BS EN ISO 14155:2020 standards and Good Clinical Practices. The conduct of the trial will be approved by the appropriate Medical Ethics Committee (MEC) of the respective clinical site and as specified by local and country specific regulations.

3.5. Subject Inclusion Criteria

Study subjects must fulfill the following clinical criteria:

- 1. Subject must be at least 18 years of age.
- 2. Subject or his/her legally authorized representative provides written informed consent prior to any clinical investigation related procedure, as approved by the appropriate Ethics Committee of the respective clinical site.
- 3. Subject must agree to undergo all clinical investigation plan-required follow-up visits and examinations.
- 4. Subjects with symptomatic leg ischemia, requiring treatment of SFA or popliteal (P1 segment) artery.
- 5. De novo or restenotic lesion(s) >70% within the SFA and popliteal arteries in a single limb which are ≥3 cm and ≤15 cm in cumulative total length (by visual estimation). Lesion must be at least 2 cm from any stented area.
- 6. Subject is willing to provide informed consent and comply with the required follow up visits, testing schedule and medication regimen.
- 7. Successful wire crossing of lesion.
- 8. Target vessel reference diameter ≥ 4 mm and ≤ 6 mm (by visual estimation).
- 9. Target lesion(s) can be treated with a maximum of two (2) CVT Everolimus-coated PTA Catheters.
- 10. At least one patent (less than 50% stenosis) tibio-peroneal run-off vessel confirmed by baseline angiography or prior MR angiography or CT angiography.

Confidential Page 17 of 79

- 11. Life expectancy >1 year
- 12. Rutherford classification of 2, 3 or 4

